#### 4.2.5.5 Analysis of SGRQ domain and total score

Change from baseline to Week 12 in SGRQ total and domain scores will be analysed using MMRM (see Section 4.1.2).

For primary analysis, LSMean change from baseline to Week 12 in SGRQ total and domain scores will be presented.

Number and proportion of participants with a decrease in SGRQ total score of  $\geq$  4 points from baseline to Week 12 (as defined in Section 3.4.4) will be summarised and analysed using chi-squared test as described in Section 4.1.4 for the ITT population.

A listing including results from each of the domain and the total SGRQ score will be produced for the ITT population.

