# 6.3 Measures to Minimise Bias: Randomization and Blinding

#### 6.3.1 Methods for Assigning Study Intervention Groups

All participants will be centrally assigned to randomised study intervention using an RTSM system and will be stratified by baseline eosinophil count ( $< 300 \text{ cells/}\mu\text{L}$ ) and background medication usage (ICS or no ICS).

Before each site is initiated, the login information and directions for the RTSM system will be provided.

Study intervention will be dispensed at the study visits summarized in SoA (Section 1.3).

The RTSM system will provide to the investigator(s) or pharmacists the kit identification numbers to be allocated.

AstraZeneca

Routines for this will be described in the RTSM system user manual that will be provided to each centre.

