# 3.1.4 Handling of missing data

No imputation for missing efficacy endpoints will be done. For the primary analysis, MMRM will be used and which, in the event of missing data, uses all data that are available.

Missing safety data will generally not be imputed. However, safety assessment values of the form of "< x" (below the lower limit of quantification) will be imputed as "0.5x LLOQ" in the calculation of summary statistics but displayed as "< x" in the listings. No imputation will be done for laboratory values of the form ">x" (above the upper limit of quantification) and the value ">x" will be displayed in the listings. Note that 0 should not be used as an imputed value in case the endpoint requires a log transformation.

In the different analyses performed, the log-transform eosinophil value can be used, a constant of 0.005 will be added to all the patients at the time of the calculation of the log eosinophil to avoid the issues due to the log-transformation.

Additionally, adverse events that have missing causality (after data querying) will be assumed to be related to study drug.

Missing ADA result at baseline data will be assumed to be negative, for other missing ADA data, no imputation is planned.

PK serum concentrations below the lower limit of quantification will be reported as NQ (Not Quantifiable) in the listings with the LLOQ defined in the footnotes of the relevant TFLs. Individual serum concentrations that are Not Reportable will be reported as NR and those that are missing will be reported as NS (No Sample) in the listings. PK serum concentrations that are NQ, NR or NS will be handled as follows for the provision of descriptive statistics:

- Any values reported as NR or NS will be excluded from the summary tables and corresponding figures.
- At a time point where less than or equal to 50% of the concentration values are NQ, all NQ values will be set to the LLOQ, and all descriptive statistics will be calculated accordingly.

- At a time point where more than 50% (but not all) of the values are NQ, the gmean, gmean  $\pm$  gSD and gCV% will be set to NR. The maximum value will be reported from the individual data, and the minimum and median will be set to NQ.
- If all concentrations are NQ at a time point, no descriptive statistics will be calculated for that time point. The gmean, minimum, median and maximum will be reported as NQ and the gCV% and gmean  $\pm$  gSD as NR.

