## 3.4.4 St George's Respiratory Questionnaire

The SGRQ is a 50-item PRO instrument developed to measure the health status of patients with airway obstruction diseases (Jones et al 1991). The SGRQ yields a total score and three domain scores (symptoms, activity, and impacts). The total score indicates the impact of disease on overall health status. This total score is expressed as a percentage of overall impairment, in which 100 represents the worst possible health status and 0 indicates the best possible health status. Likewise, the domain scores range from 0 to 100, with higher scores indicative of greater impairment. Specific details on the scoring algorithms are provided by the developer in a user manual (Jones and Forde 2009). The principle of calculation of total score and domain scores in accordance with the abovementioned user manual are provided in Appendix B 3.

The SGRQ will be completed using the eDiary in accordance with the SoA (CSP Section 1.3), and a 4-week recall version will be used.

The key outcome variable for the SGRQ will be the change in total SGRQ score from baseline to Week 12, but the change in total score from baseline to Week 4 and Week 28 will also be derived (see Section 3.1.3). Change in the domain score from baseline to Week 4, Week 12 and Week 28 will also be derived.

Other variables based on SGRQ to report include:

- Proportion of participants with a decrease in SGRQ score of ≥ 4 points from baseline to Week 12 (Yes=1/No=0)
  - Yes: change from baseline SGRQ score to SGRQ score at Week  $12: \le -4$
  - No: change from baseline SGRQ score to SGRQ score at Week 12: > -4
- Proportion of participants with a decrease in SGRQ score of ≥ 4 points from baseline to Week 28 (Yes=1/No=0)
  - Yes: change from baseline SGRQ score to SGRQ score at Week  $28: \le -4$
  - No: change from baseline SGRQ score to SGRQ score at Week 28: > -4

Participants with missing or non-evaluable SGRQ score will be considered as not achieving SGRQ response.

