# 4.1.2 Repeated measures mixed effects analysis of covariance model

The repeated measures mixed effects analysis of covariance model (MMRM) will be used to fit change from baseline for continuous endpoints at each visit, for the ITT population. For Primary Analysis, the model will include all available data from all visits up to and including Week 12, irrespective of whether the participant discontinued study intervention. Since a repeated measures model is being applied, no imputation will be made for missing data. The model will include fixed effects for baseline, log-transformed eosinophil value, background medication strata, geographical region, number of exacerbations during the previous 12 months ( $\leq$ 1 vs 2 or more), visit, study intervention and the baseline by visit and study intervention by visit interactions. An unstructured covariance matrix will be used to describe the correlations between observations on a participant between visits, and Kenward-Roger correction will be used for degrees of freedom approximation in the generation of model. In

the event that the model with unstructured covariance matrix fails to converge, and alternative such as autoregressive or compound symmetry will be used instead. Estimates of the least square mean change from baseline in  $FEV_1$  for each study intervention, and the difference between them (MEDI3506-placebo), together with two-sided 80% CI, will be obtained from the model for each visit. The significance of the study intervention effect will be tested at a 10% one-sided level of significance.

The reportable results from the model will be:

- The least-square means (LSMeans) change from baseline at each visit and their standard errors for each study intervention group
- The difference in change from baseline at certain visit between MEDI3506 and placebo (LSMeans difference) together with its two-sided 80% confidence interval (CI)
- The one-sided p-value for the difference in change from baseline at each visit between MEDI3506 and placebo

If the parameter is log-normally distributed, the variable fitted in the model will be the change from baseline in logarithmical scale, with the logarithm of the baseline value as a covariate. Change from baseline in logarithmical scale is defined as the log-transformation of the postbaseline visit value minus the log-transformation of the baseline value.

The MMRM will be as described above but the reportable results from the model will be:

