### 4.1.3 Analysis of covariance

The ANCOVA model will be used to fit change from baseline for continuous endpoints collected at only one post-baseline visit. Data used in the model are data from baseline and the scheduled tested visit. The study intervention, log-transformed eosinophil value, background medication strata, geographical region and number of exacerbations during the previous 12 months ( $\leq 1$  vs 2 or more) will be considered as fixed effects of the model while the baseline value as covariate. Comparisons of MEDI3506 CCI versus placebo will be assessed. The restricted maximum likelihood (REML) approach will be used for the estimation of the variance and covariance parameters of the linear mixed model; one-sided difference test, with alpha level at 10% will be used for the comparisons and for the t-type confidence interval calculation. No imputation will be made for missing data.

The reportable results from the model will be:

- The LSmeans and their standard errors for each study intervention group;
- The difference between MEDI3506 and placebo (LSmean difference) together with its two-sided 80% CI;
- The one-sided p-value for the difference between MEDI3506 and placebo.

If the parameter is log-normally distributed, the variable fitted in the model will be the change from baseline in logarithmical scale, with the logarithm of the baseline value as a covariate. Change from baseline in logarithmical scale is defined as the log-transformation of the postbaseline visit value minus the log-transformation of the baseline value.

The ANCOVA will be as described above but the reportable results from the model will be:

- Back transformed LSmeans for each group, which correspond to the estimated ratio to baseline; back transformed LSmeans is derived as EXP(LSMean);
- The two-sided 80% CI of the back transformed LSmeans for each group; 80% CI of the back transformed LSmeans is derived as EXP(Lower limit of the 80% CI of the LSmean); EXP(Upper limit of the 80% CI of the LSmean);
- The ratio between MEDI3506 and placebo; the ratio is calculated as EXP(LSMean difference);
- The two-sided 80% CI of the ratio; the 80% CI of the ratio is calculated as EXP(Lower limit of the 80% CI of the LSmean difference); EXP(Upper limit of the 80% CI of the LSmean difference);
- One-sided p-value.

4.1.4

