### 4.1.5 Negative binomial regression

Negative binomial regression will be used for the analysis of event rates. In this study the response variable in the model will be either the number of COPD CompEx event or experienced by a participant. The model will include study intervention group as a fixed effect and logarithm of the participant's corresponding 'at risk' time will be used as an offset variable in the model to adjust for participants having different exposure times during which the events occur. All available data from participants will be included, irrespective of whether they discontinued study intervention.

The model will include study intervention group, log-transformed eosinophil value, background medication strata, geographical region and number of exacerbations during the previous 12 months ( $\leq 1$  vs 2 or more) as fixed effects.

The standard parameterization approach (NB2) of the negative binomial model will be applied using PROC GENMOD (SAS procedure).

The estimated annual event rate (AER) for each treatment, the treatment effect (ie, the rate ratio of actual study intervention group versus placebo), corresponding two-sided 80% CI, and one-sided p-value for the rate ratio will be presented. The estimate of the negative binomial overdispersion parameter will also be reported.

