Table 14.2.1.12.1	Proportion of subjects with a decrease in SGRQ total score of >= 4 points from baseline to Week 12 treatment comparisons chi- squared test (ITT population)	AZ Respiratory CSR/HLD Table Template Q_T5 (Customization of AZ Corporate Table Template E9)	Rename column Number (%) of < <type event="" of="">>: <<type event="" of="">> is "decrease in total score of >=4 points from baseline to Week 12".</type></type>	X		X

TLF number	Title	Standard mock shell reference	Additional Information	Analysis1 (Week 12)	Analysis2 (Week 28)	Final Analysis
Table 14.2.1.12.2	CCI	AZ Respiratory CSR/HLD Table Template Q_T5 (Customization of AZ Corporate Table Template E9)		Х	X	X
Table 14.2.1.13	Airwave Oscillometry parameters by visit, summary statistics (ITT population)	AZ Respiratory CSR/HLD Table Template EF_T1a (Customization of AZ Corporate CSR/HLD Table Template E10)	
 
"Page-by" presentation for analysed variable and change from baseline in:
 
R5-R20
 
R5
 
R20
 
AX
 
CCI
 
By visit (Baseline, Week 12, CCI))
 
	X	X	X
Table 14.2.1.14.1	Change from baseline to Week 12 in Airwave Oscillometry parameters treatment comparisons, ANCOVA (ITT population)	AZ Respiratory CSR/HLD Table Template EF_T2a (Customization of AZ Corporate table template E7)	
 
"Page-by" presentation for difference in mean change from baseline in:
 
R5-R20
 
R5
 
R20
 
AX
 
CCI
 
AX
 
CCI
 
At Week 12 (MEDI3506–placebo).
 
	X		X

TLF number	Title	Standard mock shell reference	Additional Information	Analysis1 (Week 12)	Analysis2 (Week 28)	Final Analysis
Table 14.2.1.14.2	CCI	AZ Respiratory CSR/HLD Table Template EF_T2a (Customization of AZ Corporate table template E7)	CCI	X	X	X
Table 14.2.1.15	Objective cough measures by visit, summary statistics (ITT population)	AZ Respiratory CSR/HLD Table Template EF_T1b (Customization of AZ Corporate table template E10)	
 
"Page-by" presentation for analysed variable and relative change from baseline in:
 
Daily (ie, 24 hour) cough frequency
 
Night time cough frequency
 
Awake time cough frequency
 
By visit (Baseline, Week 12).
 
	X	X	X
TLF number	Title	Standard mock shell reference	Additional Information	Analysis1 (Week 12)	Analysis2 (Week 28)	Final Analysis
----------------------	---	---	---	---------------------------	---------------------------	-------------------

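### The visible SAP text tests Week 12 SGRQ response by chi-squared with no covariates; a logistic model using baseline SGRQ would be a free, modest improvement

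*SAP*

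**What the plan says.** SAP Section 4.2.5.5 gives SGRQ two Week 12 analyses. Total and domain scores go into the repeated-measures model. The responder proportion is "analysed using chi-squared test as described in Section 4.1.4 for the ITT population". The matching entry in the Appendix A output list, Table 14.2.1.12.1, reads "baseline to Week 12 treatment comparisons chi- squared test (ITT population" and mentions no covariate or stratum. The title and body of Section 4.1.4 are redacted.

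The other models state their adjustment:
- Repeated-measures model (Section 4.1.2): "The model will include fixed effects for baseline, log-transformed eosinophil value, background medication strata, geographical region, number of exacerbations during the previous 12" months, plus visit and interactions.
- ANCOVA (Section 4.1.3): the same factors, which "will be considered as fixed effects of the model while the baseline value as covariate".
- Negative binomial (Section 4.1.5): "The model will include study intervention group, log-transformed eosinophil value, background medication strata, geographical region and number of exacerbations during the" previous 12 months. The Cox model (Section 4.1.6) matches it. Neither contains a baseline value of the outcome.

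SAP Section 6 names these four models as gaining region and exacerbation history. It does not name the chi-squared test. Protocol Section 6.3.1 says that assignment "will be stratified by baseline eosinophil count" and by ICS use.

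On missing data, Section 3.4.4 says "Participants with missing or non-evaluable SGRQ score will be considered as not achieving SGRQ response", while Section 3.1.4 says in general "No imputation for missing efficacy endpoints will be done".

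**The concern.** Whether a participant falls by 4 points depends partly on the starting score. High scores tend to regress downwards, and low scores have little room to fall. Baseline SGRQ is collected and already used for the continuous endpoint, so leaving it out of the responder comparison discards a likely predictor. The visible text also gives the responder comparison no effect measure or interval, whereas the four models each report a two-sided 80% CI and a one-sided p-value.

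What is at stake is some precision, a usable effect estimate and consistency between two analyses of one questionnaire. The error rate is not at stake.

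**Working it through.** **1. The plan's own figure.** The only sample-size statement is for FEV1 (SAP Section 1.3): difference 90 mL, SD 250 mL, one-sided 10%, power 80%.

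n per arm = 2 × (1.2816 + 0.8416)² × 250² / 90² = 69.6, so 70. Power at 70 per arm is 80.2%. Allowing 2%: 140 / 0.98 = 142.9, so 143, or 144 at 72 per arm. The stated figure reproduces, and this point does not affect it. No sample size or response rate is given for SGRQ response, so everything below rests on assumed rates.

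**2. What the unadjusted comparison can detect.** With 72 per arm, one-sided 10%:

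power ≈ Φ( Δ / √{[p0(1−p0) + p1(1−p1)] / 72} − 1.2816 )

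Example, 40% versus 50%: SE = √[(0.24 + 0.25) / 72] = 0.0825; 0.10 / 0.0825 = 1.212; Φ(−0.069) = 47%.

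| Assumed placebo response | +10 points | +15 points | +20 points |
|---|---|---|---|
| 30% | 49% | 72% | 88% |
| 40% | 47% | 70% | 87% |
| 50% | 47% | 71% | 88% |

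**3. Simulation A: adjusting for baseline only.** 70 per arm, mean change -3 and -6.5, SD 13, cut at -4, 1,500 trials per scenario. Response rates are Φ(−1/13) = 47% and Φ(2.5/13) = 58%.

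| Correlation of change with baseline | Chi-squared | Logistic | Gain |
|---|---|---|---|
| 0 | 48% | 48% | 0 |
| -0.3 | 51% | 51% | 0 |
| -0.45 | 50% | 54% | 4 |
| -0.55 | 50% | 56% | 6 |

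**4. Simulation B: adjusting for baseline and two strata.** 72 per arm, mean change -3 and -7, SD 12, 3,000 trials per scenario. Response rates are Φ(−1/12) = 47% and Φ(3/12) = 60%. The stratum effect is in SD units of change.

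| Correlation | ICS-stratum effect | Chi-squared | Logistic | Gain |
|---|---|---|---|---|
| 0 | 0 | 63.2% | 62.8% | -0.4 |
| -0.3 | 0 | 63.8% | 64.5% | 0.7 |
| -0.3 | 0.4 | 62.5% | 64.4% | 1.9 |
| -0.5 | 0.4 | 64.8% | 69.8% | 5.0 |

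With no treatment effect, rejection rates over the same four scenarios were 9.8% to 11.4% for chi-squared and 9.7% to 11.2% for logistic.

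Monte Carlo standard errors for a single power figure are about √(0.5 × 0.5 / 1500) = 1.3 points in A and √(0.64 × 0.36 / 3000) = 0.9 points in B. Both tests see the same data, but differences of a point or less should still be read as nil.

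**5. What the redacted section could change.** A Cochran-Mantel-Haenszel version would account for the ICS and eosinophil strata. Baseline SGRQ, a 0–100 score, could enter such a test only after being cut into categories.

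**The case against.** The strongest objection is that the details of the test sit in a redacted section. A reader might infer that the test ignores the randomisation strata, but redacted text is not missing text, and a stratified version cannot be ruled out. A reader might also infer that chi-squared is non-directional and clashes with one-sided testing. For two groups the statistic is the square of the pooled z, so a one-sided p-value follows from the sign of the difference. Both points call for confirmation from the sponsor; neither is an established fault.

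Next, little depends on this endpoint. It is not among the four key secondary hypotheses in SAP Section 4.1.1. Section 3.4.4 makes change in total SGRQ the main SGRQ variable, and that is already adjusted for baseline. An unadjusted comparison of randomised proportions is valid. All of this stands, and it limits the point to an improvement.

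Finally, the remedy has loose ends. Neither simulation fitted the full covariate set. A participant without baseline SGRQ counts as a non-responder under Section 3.4.4 but would drop out of a logistic model. Both objections are fair, and the fix must settle the second. Week 28 is left aside because the neighbouring output entry, Table 14.2.1.12.2, is redacted.

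**Conclusion.** The point holds as a minor, optional improvement. The visible text gives the Week 12 responder comparison no covariates, and a chi-squared test would not use continuous baseline SGRQ whatever Section 4.1.4 says. The assumed gain from adjustment is about 0 to 6 power points: nil to 2 for correlations between 0 and -0.3, and 4 to 6 only for -0.45 to -0.55. Those correlations, the SDs and the response rates are assumptions.

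Three wider readings are not supported:
- A reader might conclude that this test differs from every other efficacy model. The Cox and negative binomial models also lack a baseline value of the outcome. All four main models replace the eosinophil stratum with a log value, so only the ICS stratum is kept as randomised.
- A reader might expect the two SGRQ endpoints to disagree only because one is adjusted. They also differ by dichotomising at 4 points and by handling of missing data, and either could produce disagreement.
- A reader might see Sections 3.4.4 and 3.1.4 as a real contradiction on imputation. The endpoint-specific rule governs, and only a cross-reference is needed.

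**What to change.** 1. Analyse Week 12 SGRQ response by logistic regression with study intervention, baseline SGRQ total, log eosinophils, background-medication stratum, region and prior exacerbations.
2. Report an adjusted odds ratio or a standardised risk difference, chosen in advance, with two-sided 80% CI and one-sided p-value. The risk difference stays closer to the comparison of proportions that the endpoint describes.
3. Keep the chi-squared test as supportive, and confirm whether it is stratified and one-sided.
4. Keep the non-responder rule of Section 3.4.4 and cross-reference it in Section 3.1.4 as an exception.
5. State how participants without baseline SGRQ stay in the model, for example by filling in the covariate with a single value that ignores treatment arm. The visible protocol schedule places SGRQ at SV3 and not at screening, so there may be no earlier value to use. Section 3.1.1 bars imputing baseline, so it needs the same exception.

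The cost is SAP wording and one standard model. No new data are needed, and no visible protocol text prescribes a responder test that would have to change.

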#### 4.2.5.6 Analysis of AO parameters

Observed values and absolute change from baseline to Week 12 CCI in AO parameters will be summarised by visit for ITT population.

Change from baseline in AO parameters at Week 12 will be analysed using an analysis of covariance model (see Section 4.1.3).

For primary analysis, LSMean change from baseline to

Week 12 in AO parameters will be presented.

AO parameters will be also reported in a listing.

#### 4.2.5.7 Analysis of objective cough measurements

Observed values and absolute change from baseline to Week 12 in objective cough parameters will be summarised for ITT population.

Relative change from baseline in objective cough measures at Week 12 will be analysed using an analysis of covariance model as described in Section 4.1.3. Objective cough measurements will be log-transformed prior to analysis.

Arithmetic mean together with SEM of daily, night-time and awake time cough frequencies will be plotted for Baseline and Week 12 timepoints.

Cough parameters will be also reported in a listing.

